**BLINDING**

The treating clinician and study staff could not be blinded to allocation due to the nature of the intervention, but post-discharge outcome assessors and statistical summaries for trial monitoring were unaware of group allocation. We restricted unblinded data evaluation during the trial and before setting this plan to a designated study statistician and the DSMB. We will unblind investigators and begin analyses only after all data collection forms are completed, data queries resolved, and data are locked for analysis.

**POWER AND SAMPLE SIZE**

The sample size was driven by the safety aim ( $H_2o$ ) due to the non-inferiority hypothesis and the binary nature of the outcome. The original sample size of 1,514 participants (757 per arm) was based on the differences in proportions in the composite adverse outcomes endpoint between the two arms. Our power calculations accounted for two interim analyses at approximately 1/3 and 2/3 enrollment with stopping boundaries calculated using the O'Brien and Fleming method,  $\geq 80\%$  power to reject  $H_2o$ , and a predefined 4.5% noninferiority margin. The noninferiority margin was chosen based on clinical meaningfulness and feasibility within funding constraints. It is approximately half that of the Infectious Diseases Society of America's recommendation and of two large trials of procalcitonin antibiotic guidance [10, 18].

We assumed 11% adverse outcomes by Day 30 in the usual care arm [19, 20] and a 10% loss to follow up for the original sample size estimate. We prospectively monitored both frequencies based on the overall blinded sample with intent to recalculate and adjust the sample size as necessary. The use of blinded data for the recalculation ensures that the overall significance level is 0.05. After approval by the DSMB in April 2017, the sample size was increased to 1,664 participants.

#### **IV. STATISTICAL ANALYSIS**

#### **TRIAL PROFILE**

We summarize participant flow using the Consolidated Standards of Reporting Trials diagram (CONSORT) [21-23]. The report will include number of patients screened, eligible, consented, enrolled, completed follow-up, and included in the analyses.

#### **ANALYSIS PRINCIPLES**

- We will do all primary analyses using the intention-to-treat (ITT) principle, and analyze subjects with protocol violations based on the assigned study arm, excluding only patients who withdrew consent. We will report exclusions reasons and counts by arm. For missing data, we will use multiple imputation [24] to allow standard implementation of the ITT principle [25] and to reduce bias and increase efficiency relative to a complete-case analysis [23, 26].

- Per CONSORT recommendations [22], we will also conduct per-protocol analyses in which non-protocol compliant subjects are excluded. This is deemed important because ITT may lead to false rejection of H2o, which uses a noninferiority design. Per-protocol analysis may not be the best alternative to ITT, as it may be biased when inherent differences between compliers and non-compliers exist[27]. Therefore, we will conduct sensitivity analyses by using instrumental variable [29-33] approaches to determine the complier average causal effect (CACE) [31].
- For H1o, we initially chose and conducted interim analyses based on one-sided significance levels, because we believed procalcitonin would not increase antibiotic use over an already high baseline. However, in the final analysis, we will also conduct a two-sided test to be more conservative and not rule out a potential increase in antibiotic exposure. For H2o, noninferiority testing is inherently one-sided.
- We plan pre-defined subgroups analyses irrespective of treatment effect in the overall cohort.

## **BASELINE COMPARISONS AND ASSESSMENT OF RANDOMIZATION**

We will compare the distribution of baseline variables between study arms to assess randomization success. To summarize continuous variables, we will use means and standard deviations or medians and interquartile range, and will deploy frequencies and percentages for categorical variables.

## INTERIM ANALYSES

The ProACT Coordinating Center planned to conduct two interim analyses and a final analysis using the O'Brien and Fleming stopping rules defined *a priori* controlling for an overall Type I error rate of 0.05. The first and second interim analyses occurred by plan at approximately 1/3 and 2/3 enrollment and completed in September 2016 and April 2017, respectively. The independent DSMB reviewed the results from each of the two interim analyses. Before trial completion, only the DSMB and a designated study statistician had access to unblinded data. During the interim looks, the DSMB could have recommended early trial termination due to one or more of the following reasons:

1. Efficacy - a significant difference is found for H1o and significant noninferiority for H2o, indicating decreased antibiotic exposure in the intervention arm and not worse in a combined adverse outcome point based on a predetermined noninferiority margin, resulting in a decision to stop the trial for efficacy.
2. Futility (H1o) - no difference is found for H1o based on defined futility bounds, resulting in a decision to stop the trial.
3. Futility (H2o) - a significant difference is found for H1o (i.e., decreased antibiotic exposure in the intervention arm) and a futility bound is crossed for H2o because of excess adverse outcomes in the intervention arm.
4. Failure to obtain success in the implementation of the trial either through failure to accrue subjects at the necessary rate, improper data handling, or inability to implement study protocols.

**Figure 1** provides a schematic overview of these scenarios. The stopping boundaries are shown in **Table 2**. In addition to the findings of formal hypothesis testing, the DSMB could have recommended trial stoppage due to safety concerns.

## MISSING DATA

Despite best efforts to obtain follow-up data, we anticipated some loss-to-follow-up. Optimal ITT includes analysis of data from all subjects randomized and cannot be directly adopted in the presence of missing data [25]. A complete-case analysis may lead to loss of power, and bias may be introduced when missing is not completely at random [23]. To resolve, we chose multiple imputations [24] to conduct the ITT analyses.

We will describe the extent and reasons that data are missing, summarizing the proportion of patients with missing data for each outcome and by study arm and by site. We will compare baseline patient characteristics between those who have complete outcome data and those that do not.

Multiply-imputed datasets will be generated using multivariate imputation by chained equations, an approach designed for multivariate data that can accommodate mixed data types [34]. We will use predictive mean matching and logistic regression to impute continuous and binary outcomes, respectively. We will generate 100 imputed datasets to maintain power, although 3-5 imputed datasets are usually sufficient to obtain excellent results [35].

We assume that missing outcome data are missing-at-random (MAR) in that they can be imputed reasonably well from the observed study data. We will perform imputation based on the study arm the patient was assigned to. Auxiliary variables for the imputation model will include patient baseline variables (e.g, age, sex, race, comorbidity, and condition), key ED clinician type (i.e., attending, fellow/resident, physician assistant/nurse practitioner) and study site. We will also include available intermediate outcomes, such as 15-day data to impute 30-day missing data.

## **ANALYSIS OF PRIMARY OUTCOMES**

For H1o, we will test the hypothesis that procalcitonin guideline implementation does not change antibiotic exposure by comparing the mean number of 30-day total antibiotic-days between the procalcitonin and usual care arms using a two-sample t-test, or a Wilcoxon rank sum test if data are non-normal.

For H2o, we will compare the difference in proportions of the composite adverse outcomes endpoint, relative to a 4.5% noninferiority margin, and construct a two-sided 95% confidence interval for the difference in proportions. We will declare noninferiority if the upper limit of the confidence interval is below 4.5%.

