Participants in the procalcitonin group will have one teaspoon of blood drawn for a procalcitonin level (\leq one hour after randomization goal) in the ED, and if hospitalized, 6-24 hours after the initial ED blood draw, and on Days 3, 5, and 7. Days 3, 5, and 7 blood draws for procalcitonin will only occur in hospitalized patients on antibiotics and/or at the treating clinician's discretion. For the purpose of this study, time zero is at randomization and Day 1 is defined as time of enrollment through 11:59PM of the same day.

In the ED, we will quickly (<1 hour goal) provide clinicians the procalcitonin result, accompanied by the procalcitonin antibiotic guideline (provided below). For participants who have not yet received antibiotics, we will ask the clinician to consider waiting for the procalcitonin result.

For patients admitted to hospital (or to an observation unit), we will inform the hospital clinician of the ED procalcitonin result, and that serial procalcitonin levels will be obtained, including a second one in 6 - 24 hours after the initial ED blood draw. During the hospital stay, study staff will inform clinicians when new serial procalcitonin results are available. The same procalcitonin guideline will be provided with both the initial and serial procalcitonin measurements - withhold or cease antibiotics if low, administer or continue if high.

Procalcitonin antibiotic guideline

Procalcitonin level (μ g/L)	Bacterial etiology	Recommendation
< 0.1	Very unlikely	Antibiotics strongly discouraged ¹
0.1 - 0.25	Unlikely	Antibiotics discouraged ¹
> 0.25 - 0.5	Likely	Antibiotics recommended ²
> 0.5	Very likely	Antibiotics strongly recommended ²

1. Initial antibiotics can be considered for critical illness, Legionella pneumophilia. Procalcitonin should be evaluated in context with all findings and the total clinical status; clinical judgment always necessary.

2. For outpatients, antibiotic duration based on level ($> 0.25-0.5 \mu$ g/L:3 days; $> 0.5-1.0 \mu$ g/L:5 days; $> 1.0 \mu$ g/L:7 days). Physician follow-up is recommended.

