- vii. subsequent hospitalization (for both those discharged from ED and those admitted to hospital)

v. SAMPLE SIZE

We desire at least 80% power to conduct our primary hypothesis tests using a one-sided significance level of 0.05. As shown below, determination of sample size was dependent on the hypothesis test for the primary safety outcome, as this required a larger sample size than the tests for antibiotic exposure. Analyses were performed with SAS 9.1 (SAS Institute, Inc., Cary, NC). **Allocation of 757 subjects in each arm (total trial sample size of 1514) meets our goal of at least 80% power.**

Testing H1: Procalcitonin guideline implementation reduces the total number of antibiotic-days by Day 30.

For H1, ProHOSP reduced antibiotic exposure from 8.7 to 5.7 days (35% relative risk reduction). We chose a 20% relative reduction as an appropriate minimum threshold and to detect a lower effect size than ProHOSP.

We assumed control arm antibiotic exposure of 8 days, and calculated sample size based on a two-sided two-sample test at 0.05 significance. Under these assumptions, the sample size of 1514 required for H2 provides >99% power to detect a 20% relative reduction, and 80% power to detect a reduction of as low as one antibiotic-day (12% relative reduction). Power is preserved under a wide range of assumptions. Thus, we are exceptionally well-powered for H1.

Testing H2: Procalcitonin guideline implementation does not increase the proportion of subjects who experience a composite endpoint of adverse outcomes by Day 30.

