## **SECONDARY OUTCOMES ANALYSIS**

We will follow the analysis strategies used for the primary outcomes to compare the secondary outcomes between study arms. Both ITT and per-protocol analyses will be conducted. Differences in proportions for secondary binary endpoints (antibiotic initiation by initial ED physician, ICU admission, subsequent ED visits by Day 30) will be estimated along with 95% confidence intervals. Continuous secondary endpoints (hospital length of stay, quality of life) will be compared using two-sample t-test or Wilcoxon rank sum test. Mortality at 90-days and 1 year will be estimated using Kaplan-Meier. All analyses of the secondary outcomes are considered descriptive and no formal inferences will be drawn from the secondary outcome analyses.

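### H1 is stated as a difference in mean antibiotic-days, but the SAP's test rule would probably deliver a rank-test p-value with no pre-specified difference in days and no interval

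*SAP*

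**What the plan says.** SAP, Analysis of Primary Outcomes, states that H1 is tested "by comparing the mean number of 30-day total antibiotic-days between the procalcitonin and usual care arms". The choice of test is then made to depend on the shape of the data: "using a two-sample t-test, or a Wilcoxon rank sum test if data are non-normal". The next paragraph gives H2 a two-sided 95% confidence interval for the difference in proportions. H1 is given none.

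Protocol, Sample Size, works in days throughout. It assumes 8 days in the control arm, claims "80% power to detect a reduction of as low as one antibiotic-day" and more than 99% power for a 20% reduction, and says of that effect: "We chose a 20% relative reduction as an appropriate minimum threshold".

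SAP, Missing Data, bases the intention-to-treat analysis on multiple imputation: "We will generate 100 imputed datasets to maintain power". SAP Table 2 labels its stopping boundaries as t-values, with a final H1 efficacy bound of -1.70. SAP, Blinding, fixes when analysis starts ("We will unblind investigators and begin analyses only after all data collection forms are completed") but not how normality is judged.

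Randomisation is stratified by center, race and age (Protocol, Sequence Generation; SAP, Treatment Allocation). Neither primary analysis uses these factors.

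**The concern.** The stated quantity and the test that would probably be used do not match. A t-test compares means. A Wilcoxon rank sum test asks whether values in one arm tend to exceed those in the other, and that can differ from a comparison of means when the arms differ in shape. The guideline invites such a difference, because it acts by two routes: "withhold or cease antibiotics if low, administer or continue if high". Fewer starts add zeros; shorter courses move the non-zero values.

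If the Wilcoxon branch is taken, the trial's first primary result has no pre-specified estimate in the unit in which it was designed. A reader could not tell from that result whether the reduction is near 1 day, near 1.6 days or smaller, or how precisely it is known. Two operational gaps follow: how to combine 100 rank tests, and how the combined result meets a bound written for a t-value.

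**Working it through.** **1. The protocol's H1 power.** No SD is given, so the 80% figure cannot be reproduced independently; only the SD that it implies can be found. With a two-sided 0.05 test:

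SD = 1 / [(1.96 + 0.8416) × √(2/n)]

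- 757 per arm: 6.94 days.
- 681 per arm (757 less 10% loss): 6.59 days.

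At SD 6.94 and 757 per arm, power for 1.6 days (20% of 8) is Φ(1.6 / [6.94 × √(2/757)] − 1.96) = 99.4%. The two stated powers therefore agree with each other. Both describe a comparison of means.

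**2. Would the data count as non-normal?** For assumed counts with mean about 8 and 10–40% zeros, a Shapiro-Wilk test on 1,514 values gave p below 1e-20 in every case. A formal test would select Wilcoxon, and so would an inspection of the histogram.

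**3. Do the tests address the same quantity?** In one assumed case the means were nearly equal (difference −0.06 day) but 30% of one arm and 40% of the other had no antibiotics. The t-test rejected in 5% of simulated trials and Wilcoxon in 27%.

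**4. Power under each test.** Assumptions: zero-inflated gamma counts, rounded and limited to 30 days; usual-care mean 8, SD 6.59 or 6.94, 15–35% zeros; 749 per arm (1,664 × 0.9 / 2, applying the original 10% loss to the revised size); two-sided 0.05; 2,500 trials per setting.

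| Reduction and route | Wilcoxon | t-test | Trials in which they disagree |
|---|---|---|---|
| 1 day, mixed | 79–88% | 81–86% | 3–7% |
| 1 day, shorter courses only | 67–94% | 84–88% | 4–17% |
| 1 day, fewer starts only | 81–96% | 80–83% | 3–14% |
| 1.6 days, all routes | at least 97.8% | at least 99.3% | at most 2% |

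With no effect, each test alone rejects in 4–6%. The t-test therefore holds its level at this size, and non-normality is not by itself a reason to leave the mean.

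**5. What an H1 interval would show.** The half-width is 1.96 × 6.94 × √(2/n): 0.70 day at 757 per arm and 0.67 at 832 (1,664 / 2).

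**6. Randomisation factors in H2 (minor).** The half-width is 1.96 × √[2 × 0.11 × 0.89 / n × (1 − R²)], using the original 11% event rate. R² is the share of variance that the factors explain; 0.5–10% is an assumption.

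| Per arm | Unadjusted | R² 0.5% to 10% |
|---|---|---|
| 749 | 3.17 points | 3.16 to 3.01 |
| 832 | 3.01 points | 3.00 to 2.85 |

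The gain is 1 − √(1 − R²), about 0.3% to 5% of the width.

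**The case against.** Choosing between a t-test and Wilcoxon is customary, and either test alone keeps its error rate. That stands, but it does not settle which quantity the trial estimates.

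The protocol's Statistical Methods also plan descriptive analyses, regression models that yield an estimate of treatment effect, and mixed models with center as a random effect. A reader might infer that no difference in days would ever be reported; the documents do not support that. These models are secondary to the primary tests and chosen stepwise by fit, so they do not supply a pre-specified primary estimate.

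A reader might also infer that H1 has no pooling rule at all. For a mean difference, Rubin's rules are implied by the multiple-imputation reference in SAP, Analysis Principles and Missing Data, and by the protocol's mention of Rubin's methods. Only the rank test is left without one.

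Nor does the SAP let the analyst pick whichever test rejects. Its condition refers to the distribution, so inflated type I error is not shown. The same wording recurs for continuous secondary endpoints ("will be compared using two-sample t-test or Wilcoxon rank sum test"), but those analyses are declared descriptive, so it does little harm there.

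On size, the wide power gaps need an effect by a single route and an assumed distribution; the mixed route shows little difference. The table also uses two-sided 0.05. At the one-sided −1.70 bound, the lowest Wilcoxon power for shorter courses is about 76%, not 67%. These points limit the power argument but leave the mismatch in place.

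**Conclusion.** The point holds as a gap in specification. Followed as written, the H1 rule probably leads to a rank-test p-value that does not test the stated mean. No primary difference in days, no interval, no pooling method for that test and no link to Table 2 would have been fixed in advance.

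The main consequence is interpretation. The choice of test would rarely change the conclusion at 1.6 days. It could change it in either direction at 1 day, the smallest effect for which the protocol claims 80% power. These sizes rest on an assumed shape and on the implied SD of 6.6–6.9 days; the specification gap does not depend on them.

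A reader might infer that the stated power is wrong, or that leaving out the randomisation factors makes either primary analysis invalid. Neither follows. The two power figures are mutually consistent and only lack a stated SD. The unadjusted analyses are valid and slightly conservative.

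**What to change.** Before unblinding, amend SAP, Analysis of Primary Outcomes, as follows.

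- **H1 primary analysis, whatever the distribution:** the difference in mean 30-day antibiotic-days with a 95% confidence interval, from a linear model with robust standard errors, adjusted for center, race and age as used in randomisation and pooled over the 100 imputed datasets by Rubin's rules. State that the pooled estimate divided by its standard error is the statistic set against the final H1 bound in Table 2.
- **H1 supportive analyses:** the unadjusted t-test, for continuity with the two interim looks, and Wilcoxon, with its pooling method named.
- **H2, a minor and nearly free improvement:** compare with 4.5% the confidence interval of a risk difference standardised over the same factors, and report the unadjusted interval alongside.

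If only one change is made, it should be naming the H1 mean difference and its interval.

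The cost is SAP wording and a little code, since the factors are already recorded. The real downside is lower H1 power than Wilcoxon if the effect is mainly fewer starts: 80–83% against 81–96% for a 1-day reduction in the illustration. Moving to an adjusted final H1 analysis after unadjusted interim looks costs little. With the Table 2 H1 efficacy bounds and futility ignored, overall one-sided error is 4.8–5.05% for R² of 0–10%. A simulation of the H1 model with 14 centers, assumed race and age groups and 10% loss gave two-sided error of 4.8% and 5.2%. It used complete cases, so the imputed version should be checked before it is adopted.

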**TABLE 2 – INTERIM ANALYSES T-VALUE STOPPING BOUNDARIES**

Interim	H1o		H2o		$\alpha$ – spending*
Look	Efficacy	Futility	Efficacy	Futility	
1	< -3.21	> 1.64	< -3.26	> 0.55	0.001
2	< -2.15	> -0.49	< -2.16	> -0.87	0.016
Final	< -1.70	> -1.70	< -1.71	> -1.71	0.034

\* Overall  $\alpha = 0.05$ ; Stopping boundaries represent one-sided tests for significance. Two-sided tests will also be conducted in the final analysis.

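### The SAP has two different final cut-offs for H2 non-inferiority (1.71 and 1.96), and the claimed 80% power at 1,514 holds under only the first

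*SAP*

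**What the plan says.** - **Decision rule in the text.** SAP, Analysis of Primary Outcomes: for H2 the analysts will "construct a two-sided 95% confidence interval for the difference in proportions. We will declare noninferiority if the upper limit" lies below 4.5%.
- **Decision rule in the table.** SAP Table 2 has a row for the final look. For H2 it gives efficacy below -1.71 and futility above -1.71, with overall alpha 0.05. Its footnote reads "Stopping boundaries represent one-sided tests for significance. Two-sided tests will also be conducted in the final analysis".
- **Error rate and sidedness.** SAP, Interim Analyses, describes O'Brien-Fleming rules "controlling for an overall Type I error rate of 0.05". SAP, Analysis Principles, says of H2 that "noninferiority testing is inherently one-sided". The added two-sided test is explained there for H1: "in the final analysis, we will also conduct a two-sided test to be more conservative".
- **Power.** Protocol, Sample Size: "We desire at least 80% power to conduct our primary hypothesis tests using a one-sided significance level of 0.05". The same section says that 1,514 patients give at least 80% power for the 4.5% margin when the true difference is zero, and that about 10% loss is already included. SAP, Power and Sample Size, confirms that "The original sample size of 1,514 participants (757 per arm) was based on the differences in proportions in the composite adverse outcomes endpoint", adds that the calculation allowed for both interim looks, and reports that after DSMB approval in April 2017 "the sample size was increased to 1,664 participants".

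**The concern.** A two-sided 95% interval is a one-sided test at 0.025, with critical value 1.96. The Table 2 bound of -1.71 has nominal one-sided p = 0.044. These are different tests of the same hypothesis at the same look, and no sentence ranks or links them. A final statistic between -1.96 and -1.71 would be non-inferior by the table and not by the text. For the primary safety claim, the choice would then be open after the data are seen, which the SAP exists to prevent.

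The power statement is also affected. It is given at one-sided 0.05, whereas the only sentence that declares non-inferiority uses the stricter 1.96.

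**Working it through.** **Inputs.** Event rate 11% in both arms, margin 4.5 points, true difference 0 and 10% loss inside 1,514 (Protocol, Sample Size; SAP, Power and Sample Size). Looks at 1/3 and 2/3. H2 interim bounds from Table 2: efficacy -3.26 and -2.16, futility 0.55 and -0.87.

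**What -1.71 means.** 1 - Φ(1.71) = 0.0436, and 1 - 2 × 0.0436 = 0.913. The matching two-sided interval is therefore 91.3%.

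**Single-look power at 1,514.**
- Evaluable per arm: 757 × 0.9 = 681.3.
- SE = √(2 × 0.11 × 0.89 / 681.3) = 1.695 points.
- Drift = 4.5 / 1.695 = 2.654.
- Cut-off 1.71: Φ(2.654 - 1.71) = 82.8%.
- Cut-off 1.96: Φ(2.654 - 1.96) = 75.6%.

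**Three-look power.** Simulated with the Table 2 bounds, several million runs per setting. The lower figure treats futility as binding and the upper one ignores it. The SAP does not say which applies.

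| Total and loss | Final 1.71 | Final 1.96, interim efficacy bounds kept | Final 1.96, interval as the only efficacy rule |
|---|---|---|---|
| 1,514, 10% loss | 80.8–83.3% | 75.7–77.1% | 74.1–75.6% |
| 1,514, no loss | 84.3–86.7% | 79.8–81.2% | 78.5–79.9% |
| 1,664, 10% loss | 84.0–86.3% | 79.4–80.8% | 78.0–79.5% |

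The claim of at least 80% at 1,514 reproduces under 1.71 and fails under 1.96. With 10% loss, 80% under 1.96 needs about 1,631 to 1,693 patients if the interim efficacy bounds are kept, and 1,688 to 1,749 if the interval is the only efficacy rule.

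**Where the rules disagree at 1,664 with 10% loss.** 832 × 0.9 = 748.8 per arm, so SE = 1.617 points.
- Table 2 passes if the observed excess is below 4.5 - 1.71 × 1.617 = 1.73 points.
- The 95% interval passes only below 4.5 - 1.96 × 1.617 = 1.33 points.
- With the interim bounds in use, the chance of ending between the two is about 5–6% if the true difference is 0 and 7–8% if it is 1 point.

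**Overall one-sided error for H2.** 0.044–0.048 with a final 1.71, and 0.031–0.032 with a final 1.96 and the interim bounds kept.

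**Event-rate sensitivity (assumed rates).** The rates behind the increase to 1,664 are not given. At 1,664 with 10% loss, power under 1.96 is 81–84% at 10% events, 75–78% at 12% and 72–75% at 13%.

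**H1, secondary.** The protocol names a one-sided 0.05 level for the primary tests but sizes H1 on a two-sided 0.05 test. Table 2 gives H1 a one-sided final bound of -1.70, and a two-sided test is added. After interim bounds of -3.21 and -2.15, a final 1.96 test has lower-tail error 0.032, not 0.025. Total error is 0.032 if futility is binding and 0.057 if it is ignored. A final value of about 2.15 brings the lower tail to 0.025.

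**The case against.** The best defence is that the text already settles the matter. Analysis of Primary Outcomes is the only place that says when non-inferiority will be declared. Table 2 is titled as interim stopping boundaries, and its footnote about two-sided tests is not limited to H1. On that reading the final row needs only a cross-reference. The interval rule is also conservative, 1,514 has been superseded, and the low ends of the ranges depend on binding futility or on dropping interim efficacy stopping. With interim efficacy bounds kept and futility advisory, 1,664 gives 80.8%. Imputation using Day 15 data, together with events taken from medical records, may recover some of the 10% loss.

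Much of this stands. The 95% interval is the more natural reading, it does not inflate error, and the shortfall at 1,664 is marginal under the original rates. The simulation also ignores the rule that H2 is tested at an interim only after H1 is rejected, but that gate moves power towards the single-look values, which lie inside the ranges shown.

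It does not remove the conflict. Table 2 has an explicit final row with a complete pass/fail rule for H2. The SAP explains the two-sided addition for H1 only and calls H2 one-sided. The stated power reproduces under the table's rule. Reading 1,514 as sized at 1.96 with no loss gives about 80%, but that contradicts both the stated one-sided 0.05 and the stated loss allowance.

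**Conclusion.** The concern holds. The SAP has two final rules for the primary safety decision, and the power claim fits the one that the text does not use to declare non-inferiority. At 1,514 with the stated 11% events and 10% loss, power is 80.8–83.3% under -1.71 and 74.1–77.1% under the 95% interval. At 1,664 under the same rates, interval-rule power is 78.0–80.8%. Present power cannot be settled without the rates used in the recalculation. The rules disagree over about 0.4 points of observed difference. The defect is an undefined decision and a mismatched power statement, not excess false non-inferiority. It must be fixed because it governs the primary safety conclusion. The H1 ambiguity is secondary, and this conclusion does not depend on it.

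**What to change.** Before treatment assignment is unblinded, state one final H2 rule.

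1. **Keep the 95% interval.** Mark the final H2 row of Table 2 as superseded and restate power: about 74–77% at the original 1,514, and about 78–81% at 1,664 if 11% events and 10% loss still hold, otherwise with the recalculation inputs. This is the simpler choice, because it leaves the declared standard for the safety claim unchanged after both interim looks.
2. **Keep -1.71.** Replace the 95% interval in Analysis of Primary Outcomes with the matching 91.3% two-sided interval. The power statement then stands, but the safety claim rests on a less strict interval than the text now declares.

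In either case, say whether the futility bounds are binding and give the event and loss rates behind 1,664. For H1, say whether the one-sided -1.70 bound or the two-sided test decides. If the two-sided test decides, use a final value of about 2.15; otherwise label it supportive.

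The cost is a few sentences and one power line, with no extra patients. Under the first option the stated power becomes less favourable.
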